^a = data collected during phone call (vs REDCap)

Phone Orientation Visit. Study personnel will call the participant at their scheduled session time and provide a detailed description of the study and obtain verbal consent. A copy of the informed consent and a PowerPoint describing the study in detail will be mailed and/or emailed to participants before the orientation session. If the participant decided to consent to the study, a series of self-report questionnaires to complete will be emailed to them (see Aim 3 below). Individuals who are ineligible or decline to participate will receive self-help materials and referrals for smoking cessation and alcohol use programs.

Zoom Orientation Visit. Consented participants will be scheduled for a group Zoom Orientation session one week before the first treatment session. Prior to the visit, participants will be provided a packet of instructions on how to access and navigate the video-conferencing app, Zoom, and additional materials related to the study (e.g. session handouts, welcome materials). Tablets, webcams, and/or microphones will be provided to participants on an as-needed basis. This orientation session will take place via Zoom. During this session, participants will be provided with a training on how to use video-conferencing app and will discuss the other relevant materials sent to participants in preparation for the first treatment visit. Prior to all Zoom visits in the study, participants will join a waiting room before they are admitted to the group, where they will see banners with reminders about sessions content, privacy standards, etc. This procedure will be followed for all treatment sessions as well as the Zoom Orientation session.

Randomization. Three stratification variables will be included: gender (men vs women), race/ethnicity (non-Hispanic White vs Other), and smoking rate (20+ cigarettes per day [CPD] vs less than 20). Within these 8 cells, eligible participants will be assigned to the two treatments using balanced-permuted block randomization with a block size of 4.

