Compensation and Retention Procedures. Participants will be financially compensated for completing the assessment measures, and for the costs associated with participation such as child care, etc. Participants will receive a \$10 gift card after completing measures sent after the Orientation visit, and will receive an additional \$5 bonus gift card if they complete it in 24 hours. Participants who decline to consent to the study during the Orientation visit will receive a \$10 gift card. Participants will receive \$10 for completing the Zoom Orientation visit. For measures completed prior to visits 1-4, 6, and 7, participants will receive a \$5 gift card, and a \$5 bonus gift card if they complete them within 24 hours.. For measures completed prior to visits 5 and 8, participants will receive a \$20 gift card, and a \$10 bonus gift card if they complete the measures

within 24 hours. For completing the phone call assessment prior to visits 5 and 8, participants will be compensated with a \$15 gift card. Payment for these visits differ based on the length (e.g., participants are compensated more when asked to complete lengthier questionnaire packets). Participants will be compensated with a \$20 gift card for completing the first follow-up call and measures, and will receive a \$10 bonus gift card if they complete the measures within 24 hours. For completing the second follow-up call (16 weeks post-cessation), participants will receive a \$25 gift card. Participants will receive a \$10 bonus for sending back a saliva sample to confirm tobacco abstinence. For any unreturned iPads after a period of two months of phone calls/emails from staff, a \$50 gift card incentive will be offered for the return of the iPad.

This payment schedule will apply only to Aim 2. We will also conduct the following procedures to reduce attrition: reminder phone calls or texts prior to all study visits, flexible scheduling of the group sessions (e.g., evenings, various days of the week) to accommodate different schedules, requiring a functioning phone number and home address to contact participants by phone or mail as needed, and obtaining the name, address, and phone number of at least 2 collaterals (i.e., relatives, friends) who can provide contact information for the participants, should we be unable to contact them during the study. Participants who are unable to complete the measures or phone assessments will be mailed the materials to complete.

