Negative Affect/Depression/Stress/Anxiety Measures. Center for Epidemiological Studies Depression Scale (CESD) is a 20-item self-report questionnaire that assesses depressive symptoms experienced within the past week.¹⁶⁵ Distress Tolerance Scale (DTS) is a 15-item, Likert-scale self-report measure of an individual's perception of his/her own emotional distress tolerance.¹⁶⁶ Perceived Stress Scale (PSS) is a widely used self-report measure that assesses the degree to which participants find their lives to be stressful.¹⁶⁷ Positive and Negative Affect Scale (PANAS) is a 20-item self-report Likert-scale measure that assesses an individual's positive and negative affect at a given point in time.¹⁶⁸

Alcohol and Smoking Outcomes. Alcohol Use. The Timeline Followback (TLFB)¹⁷¹⁻¹⁷³ will be used to determine daily, recent alcohol use via retrospective self-report. A calendar is provided to participants, and they indicate any key events that occurred on certain dates to aid their memory. Participants then indicate how much alcohol they drank on each day. The TLFB has been widely used, evaluated, and has strong psychometric properties.¹⁷¹⁻¹⁷³ The TLFB will collect alcohol use from the past 4 weeks at the phone screen. The TLFB will be administered at each of the following visits and will ask participants to report their use since the last time they completed the TLFB: before visits 4 and 8, and at the 8-week and 16-week follow-up. From the TLFB, the primary outcome measure derived will be the percent of heavy drinking days (defined as: on a single occasion, ≥ 5 drinks for men and ≥ 4 drinks for women). Other alcohol use outcomes, such as percent days' abstinent and alcoholic drinks per drinking day, will also be derived.

Smoking Abstinence. To determine smoking abstinence, we will use the 7-day point prevalence, which is a combination of a self-report of no smoking in the last 7 days, combined with a biochemical verification of abstinence via saliva cotinine. Participants who report abstinence will be mailed a saliva cotinine kit to confirm abstinence at their 16-week follow-up call. The TLFB will be used to collect tobacco use throughout the study, and the schedule will mimic that used to collect alcohol use.

G. Data Management and Statistical Considerations for Study 2

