A similar approach to analysis will be taken for the primary outcomes (the distal measures). TLFB will be used to derive a measure of heavy alcohol use and the 7-day point prevalence will be created for smoking abstinence at five targeted 1-week periods prior to a session: start of treatment (week -4), quit date (week 0), end of treatment (week +3), and two follow-ups (week +8 and week +16). Descriptive statistics will be presented in figures. GEE with an AR(1) working correlation matrix ($r=.60$) will be used to assess the effects of treatment, time (-4, 0, +3, +8, +16), and their interaction on the primary outcome measures. Means, percentages, and 95% confidence intervals will provide useful guidance as we determine sample sizes for a full-scale RCT. There is not adequate power to detect small- to medium-sized treatment group differences given the sample size. However, we would interpret any within-subject decreases in the number of heavy drinking days from pre- to post-treatment and/or any within-subject increases in smoking abstinence as evidence that the MBRP-SA intervention may be beneficial for these two problematic health behaviors. Given the small sample size, these changes are not likely to be significant. However, sample means and standard deviations will provide valuable data for

estimating sample size in a large-scale RCT. Changes in craving, self-efficacy, and general use of alcohol and smoking will also be examined as proximal outcomes that will also inform the development of a large-scale trial.

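### The mid-treatment Timeline Followback is scheduled before visit 4, but the payment text and the week-0 analysis window both require a call before visit 5

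*Combined protocol and SAP*

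**What the plan says.** Four places in the combined protocol and SAP bear on the timing of the in-treatment TLFB in Aim 2.

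- **Alcohol and Smoking Outcomes (Aim 3).** The baseline recall is fixed first: "The TLFB will collect alcohol use from the past 4 weeks at the phone screen". Later administrations fall "before visits 4 and 8, and at the 8-week and 16-week follow-up", and each "will ask participants to report their use since the last time they completed the TLFB". For tobacco use, "the schedule will mimic that used to collect alcohol use", so both distal outcomes share this timing.
- **Compensation and Retention Procedures (Aim 2).** The payment clause reads "For completing the phone call assessment prior to visits 5 and 8, participants will be compensated". No paid call before visit 4 is mentioned.
- **Table 4.** The TLFB entries carry the footnote "data collected during phone call (vs REDCap"). The header puts Tx 4 at week -1, Tx 5 at week 0 (quit day) and Tx 8 at week +3.
- **Aim 3 analysis, distal measures.** Heavy drinking and 7-day abstinence are derived for five one-week periods, each leading up to a session. After the start of treatment (week -4) these are "quit date (week 0), end of treatment (week +3), and two follow-ups (week +8 and week +16"). The GEE uses the same five time points.

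**The concern.** A TLFB looks backward. A call before visit 4 can report nothing about the week between visit 4 and visit 5, and that is the week the analysis assigns to the quit date. The payment text describes the phone assessment as coming before visit 5. Staff working from the outcomes section would therefore call a week earlier than the payment text provides for, and before the week-0 window has begun.

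Week 0 is one of five planned time points for outcomes that the analysis section calls primary. Saliva cotinine is tied to the 16-week call, so no biochemical measure at week 0 could stand in for the TLFB. The quit attempt and the drinking goals both start at Session 5. With calls before visits 4 and 8, a single recall interval straddles that change; a call before visit 5 separates the two periods. The plan intends to use these means, percentages and standard deviations to size a full trial.

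**Working it through.** The plan states no figure on this point, so there is none to reproduce. The check maps calls to windows.

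**Inputs.** Visit-to-week mapping from Table 4: visit k falls at week k - 5, so visit 4 = -1, visit 5 = 0 and visit 8 = +3. Follow-up calls are at weeks +8 and +16. Each analysis window is the week ending at the named time point. N = 64 (Aim 2 overview). Planned retention to end of treatment is 80% (Table 5).

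**Assumption.** Each in-treatment call takes place right before its visit. The documents give no number of days, and a call made some days earlier would shift the lags by that amount.

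**Recall lag.** For a window from a to b, take the first call at time c with c at or after b. The newest day is recalled c - b weeks back and the oldest c - a weeks back.

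| Window (weeks) | Calls before visits 4 and 8 | Calls before visits 5 and 8 |
|---|---|---|
| -5 to -4 | call at -1: 3-4 weeks | call at 0: 4-5 weeks |
| -1 to 0 | call at +3: 3-4 weeks | call at 0: 0-1 week |
| +2 to +3 | call at +3: 0-1 week | call at +3: 0-1 week |
| +7 to +8 | call at +8: 0-1 week | call at +8: 0-1 week |
| +15 to +16 | call at +16: 0-1 week | call at +16: 0-1 week |

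Under the visit 4 schedule the mid-treatment call ends at week -1, exactly where the week-0 window starts, so the overlap is zero.

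**If the call before visit 8 is missed.** A participant reached at week +8 reports the week-0 window at 8 - 0 = 8 to 8 - (-1) = 9 weeks. The window is missing only if no TLFB is completed after visit 4.

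**Size of the extra loss.** Planned non-retention at end of treatment is (1 - 0.80) × 64 = 12.8, about 13 participants. This is a ceiling. It includes people who leave before visit 5, who could equally miss a call placed there, and people who are reached at a later follow-up. The loss due to timing is limited to those who would complete a call before visit 5 but give no TLFB from visit 8 onward. The documents do not give that number, so the range is 0 to about 13.

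**The case against.** The strongest reply is that visit 4 is simply a wrong number in one sentence and no data would ever be affected. The payment text and the week-0 window both support that. So does the TLFB row of Table 4: in the text available for this review, its mid-treatment mark sits three columns before the next mark, the same gap as between the quit-day and end-of-treatment marks in the smoking-scale rows. Visit 4 would give a gap of four. That row has lost columns in extraction, so this is suggestive and not decisive. If the reply is right, the harm disappears once the sentence is corrected, but the correction is still needed.

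Other points on that side:

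- **The link to payment is inferred.** The compensation section does not name the TLFB as the paid call. The connection comes from the phone footnote in Table 4, which also marks the alcohol use goals. This stands, but the conflict with the week-0 window does not depend on it.
- **Three to four weeks is not unusual recall here.** The phone screen itself uses a 4-week recall. This stands, and it makes the recall harm moderate.
- **Stakes are limited.** Study 2's primary outcomes are the Table 5 benchmarks, Aim 3 is declared underpowered, and the week-0 window precedes the quit day, so it says little about abstinence. GEE keeps participants with partial data, although that does not remove bias from informative dropout. This stands and lowers the priority.

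A reader might infer that week-0 data are lost for everyone who leaves between visits 4 and 8. The documents do not support that. Each TLFB covers the time since the last one completed, mailed materials are offered to those who cannot complete measures or calls, and leaving the group sessions is not the same as missing a later call.

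**Conclusion.** The plan is wrong as written, as an internal inconsistency. The outcomes section sets a call that cannot capture any of the week-0 window, while the payment section and the distal-outcome analysis both point to visit 5. If the outcomes section is followed, week-0 heavy drinking and smoking rest on 3-4 week recall instead of 0-1 week, or 8-9 weeks if the next completed TLFB is the week +8 call. They are missing only where no TLFB follows visit 4.

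It would be tempting to read about 13 of 64 as the expected loss. It is only the upper end of an unknown range starting at 0, and it assumes the planned 80% retention. The lags assume calls made right before the visits. The stakes are modest because Aim 3 is descriptive, but the error touches a planned time point for both distal outcomes and is nearly free to correct.

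**What to change.** In the section on alcohol and smoking outcomes, change the in-treatment TLFB timing from visits 4 and 8 to visits 5 and 8. This matches the payment text and the week-0 analysis window and applies to both the alcohol and the tobacco TLFB. Confirm that the mid-treatment TLFB mark in the intact Table 4 sits under week 0, and state in the compensation section that the paid call includes the TLFB.

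The cost is a change of wording, with the same number of calls and payments. The one downside is that the start-of-treatment window (week -4) is recalled 4-5 weeks back instead of 3-4, which is slightly beyond the 4-week recall used at the phone screen.

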Treatment Overview. All participants will receive nicotine replacement therapy (NRT) and either MBRP-SA or CBT. Table 4 provides an overview of all treatment and follow-up visits.

NRT. The nicotine transdermal patch is the most widely used pharmacotherapy and the Treating Tobacco Dependence Clinical Practice Guideline has identified it as frontline therapy.¹⁴² The patch is safe, tolerable, and available over-the-counter. Patch therapy for participants who smoke >10 CPD will consist of 6 weeks of 21 mg patches and 2 weeks of 14 mg patches. Patch therapy for participants who smoke 5-10 CPD will consist of 6 weeks of 14 mg patches and 2 weeks of 7 mg patches. Patch dispensation will occur at weekly treatment visits. Participants receive only the number of patches needed to last until the next visit plus several extra patches should one fall off, become torn, etc, or should the visit be delayed. Based on our previous research, compliance is improved when participants are provided with only enough patches to last until the subsequent visit. A reduction in dosage or cessation of the patch regimen will be implemented for any participants who show signs of being on too high of a dose, which is expected for very few participants since blood nicotine levels are usually much lower on the patch than while smoking. Note that for Aim 2, patches will be mailed each week.

MBRP-SA and CBT. MBRP-SA was already described above. CBT is a well-established and commonly used treatment for substance use behaviors that primarily utilizes a problem solving and coping skills approach rooted in relapse prevention theory,¹⁵² combined with standards from the Guideline.¹⁴² Session content will generally follow the manual used in the original MBRP RCT⁶⁴, the MBAT RCT⁵⁸, and standards from the Guideline (e.g., setting a quit date, providing NRT).¹⁴² CBT will consist of 8 sessions (2 hours each), with 8-10 participants in each group. Thus, participants in both MBRP-SA and CBT will be matched on treatment contact time. All treatment activities focus on promoting/maintaining smoking abstinence and reducing drinking, with specific treatment objectives for each session. Participants will receive weekly emails that outline the group session as well as include relevant links and attached handouts for their review. Participants will also receive referrals for mental health and substance use at the end of treatment.

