3.4 Investigator Study Files

Research records for patients on this study are the responsibility of the investigator. They will be available for review by the sponsors of the trial, health care personnel involved in this study, the IRB, DHHS, and the FDA.

Sources of Materials

Data collected from participants for research purposes include a saliva testing for Cotinine (a nicotine metabolite) and self-report measures and interview data that collect demographic, medical history, psychiatric symptoms, smoking-related information, alcohol-use information, and questions about personality traits and current affective and cognitive states. Data will be collected electronically via REDCap. The treatment sessions for the MBRP-SA group involve mindfulness (meditation) practice that is tailored to smoking cessation and reducing alcohol use. The treatment sessions for the CBT group involve coping and reappraisal skill training that is tailored to smoking cessation and reducing alcohol use. Participants will be asked about the feasibility and acceptability of the treatments, in addition to monitoring their homework practice each week.

Potential Risks

Minimal risks are anticipated for this study. Data including self-report, interview (psychological and medical), and biological samples (e.g., saliva) involve risk of breaches in confidentiality. Although everyone will be asked to keep the information shared during the group sessions confidential and to maintain anonymity outside of sessions, a breach of confidentiality is always possible. Participants will always be given the option to refuse to answer any questions on the measures that may be distressing. Successful abstinence may cause irritability, anxiety, general distress and difficulty concentrating. The nicotine patch that participants will wear beginning on the quit date will be the appropriate dose for their level of smoking, and the patch should aid in the management of withdrawal symptoms. The nicotine patch and smoking cessation counseling have been shown to be safe and effective for smokers attempting to quit. However, side effects to the patch may occur and include skin irritation/ rash, nausea, dizziness, dry mouth, diarrhea, nervousness, headache, vivid dreams or sleep disturbances, irritability, and irregular heartbeat.

Protections Against Risks

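### Week-16 abstinence is verified by cotinine alone and no named item records nicotine-medication use, so a non-smoker using such medication can be scored as not abstinent

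*Combined protocol and SAP*

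**What the plan says.** Under Aim 3, Smoking Abstinence, the 7-day point prevalence is "a self-report of no smoking in the last 7 days, combined with a biochemical verification of abstinence via saliva cotinine". Sampling is confined to the last contact: "Participants who report abstinence will be mailed a saliva cotinine kit to confirm abstinence at their 16-week follow-up call". The Compensation text describes the same step as "sending back a saliva sample to confirm tobacco abstinence". Section 3.4, Sources of Materials, lists "saliva testing for Cotinine (a nicotine metabolite" in its own parenthesis, so the protocol itself identifies the analyte as a product of nicotine.

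The NRT paragraph gives patches to participants in both arms: 6 weeks at one dose and 2 at a lower one. Patches are dispensed weekly in the number needed until the next visit, "plus several extra patches should one fall off, become torn, etc, or should the visit be delayed". The same paragraph notes that patches are sold over the counter. Under the Aim 1 content modifications, patch use starts at Session 5, the quit day.

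Smoking at follow-up is recorded by the Timeline Followback (TLFB): "The TLFB will be used to collect tobacco use throughout the study". Use of cessation medication is named once, as an exclusion at entry (section 1.2).

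The Aim 3 analysis text treats week-16 abstinence as one of its distal outcomes and says the percentages and confidence intervals will inform the sample size of a full trial.

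**The concern.** Cotinine shows exposure to nicotine and does not identify the source. A participant who has stopped smoking but is using a patch or another nicotine product as medication at week 16 can return a positive sample. Under the stated definition that person is not a verified abstainer. The rule is conservative and clear, but the plan names nothing that would show how often it catches non-smokers, and that information cannot be recovered once the call has passed.

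What is at stake is the week-16 verified abstinence rate, which is meant to help plan the next trial. The error can go only one way: true non-smokers are counted as not abstinent, and the rate is understated.

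**Working it through.** No sample-size figure is in dispute, so the check sets the relevant texts side by side and then sizes one misclassification.

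**1. Is there another marker?** Table 3 (Aim 1) lists carbon monoxide. Table 4 (Aim 2) lists saliva cotinine as the only biochemical test.

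**2. Is nicotine medication recorded at week 16?** As Table 4 can be read, the week-16 items are Alcohol Use Goals, TLFB and saliva cotinine. The payment text agrees: week 8 carries a "gift card for completing the first follow-up call and measures", while week 16 pays for the call alone ("For completing the second follow-up call (16 weeks post-cessation), participants will receive a" a set amount). The TLFB is described as covering alcohol and tobacco. The question on other tobacco products belongs to Smoking Use and History, which is scheduled at orientation only, and its examples are not medications. No named week-16 item covers patch or other nicotine medication.

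**3. How would such a participant be classified?** The definition needs self-report and verification together. Self-report of no smoking with a positive sample is therefore not verified abstinence.

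**4. Can the study's own patch course overlap the test?**
- Planned course: 6 + 2 = 8 weeks from the quit day = 56 days.
- Week-16 call: 16 × 7 = 112 days, window ± 5 days, so the earliest is 112 − 5 = 107 days.
- Gap: 107 − 56 = 51 days at the least.

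Use on schedule does not overlap the test. What remains is late or interrupted use, leftover patches (return of spares is not described), and products the participant buys.

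**5. Size of one error.** With 64 randomized 1:1, an arm has 64/2 = 32. One misclassified participant moves the arm's week-16 rate by 1/32 = 3.1 percentage points, always downward.

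**6. Illustration only.** The documents give neither the abstinence rate nor the share of abstainers on nicotine medication at week 16. Assume 25% true abstinence (8.0 of 32), 5% to 20% of abstainers on such medication, and every one of them testing positive. The last assumption pushes the result upward.
- Recorded rate = 25% × (1 − f).
- f = 5%: 23.75%, or 7.6 of 32.
- f = 20%: 20.0%, or 6.4 of 32.
- Shift: 1.25 to 5.0 points.

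**7. Set against sampling error.** The 95% half-width for one arm is 1.96 × √(p(1 − p)/32). At p = 20% it is 13.9 points, and at p = 30% it is 15.9 points.

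**The case against.** The strongest reply is that the plan already deals with the matter. Requiring both self-report and cotinine is a rule, and a defensible conservative one. A reader might infer that the protocol leaves cotinine-positive self-reported abstainers unclassified. It does not; they are not verified. This part of the objection stands, and the main analysis need not change.

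A reader might also infer that the trial's own patches spoil its own test. The 51-day gap answers that for anyone who follows the schedule, and the weekly limit on supply restricts stockpiling. What stands against the plan is narrower: off-schedule and self-bought use is possible and goes unrecorded.

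The NRT paragraph says that patch wearers usually have much less nicotine in the blood than smokers, so some users might test negative. That helps only with a saliva cut-off chosen to separate the two groups, and none is stated. It is still a reason not to assume that every user would test positive.

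Staff might ask about medication on the call without a listed item, and the call scripts are not reproduced. That is possible. Even so, nothing in the plan makes use of the answer.

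Finally, the plausible effect is smaller than the sampling error at 32 per arm, and Aim 3 is declared underpowered. Both statements are correct and they limit the weight of the point. But sampling error falls on either side of the truth, whereas this error has one direction and would recur in a larger trial that reused the procedure.

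**Conclusion.** The point holds and is minor. Week-16 abstinence can be understated because a non-smoker using nicotine medication may fail cotinine verification, and no named item would reveal it. The size is 3.1 percentage points per misclassified participant in an arm of 32. How many there would be is unknown, and the documents support no estimate.

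Two larger conclusions are not supported. First, a reader might infer a biased comparison between MBRP-SA and CBT. Both arms receive the same patches, and nothing in the documents points to different late use. Second, a reader might infer that the feasibility findings are at risk. The benchmarks in Table 5 are the stated primary outcomes of Study 2, and none depends on cotinine. The effect is confined to one time point of a descriptive aim.

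The conclusion rests on two readings: that Table 4 lists no other week-16 item, which the payment text supports, and that the TLFB records tobacco but not medication, as it is described.

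**What to change.** On the week-16 call, ask participants who report abstinence whether they used a patch or any other nicotine medication in the last 7 days, the same window as the abstinence definition.

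Keep the present rule as the main result: a positive sample is not verified abstinence. Add one table row in which cotinine-positive self-reported abstainers who report nicotine medication are counted as abstinent, and give the number of such participants per arm.

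The cost is one question on a call that already takes place, one sentence in the Smoking Abstinence paragraph, and one table row. The saliva kit, sample size and patch advice are unchanged. The drawback is that reported medication use could mask smoking, so the added row should be labelled an upper bound and should not replace the main result.

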To ensure participant confidentiality, no unique identifiers will be recorded into the dataset to be analyzed. Data will be collected via REDCap. The entered and reviewed data will be transferred monthly to a SPSS database.¹⁷⁴

Sample Size. Randomizing 64 participants to MBRP-SA and CBT will provide sufficient data for assessing feasibility of the RCT, based on existing recommendations in the literature for sample size estimates in feasibility studies.^{175,176} A full set of statistical analyses focusing on treatment differences will be performed as part of the feasibility assessment. However, the sample size will not be sufficient for detecting treatment differences for anything less than large effect sizes (e.g., Cohen's $d \geq .72$) for simple, two-group comparisons of a continuous variable with $\alpha=.05$, power $\geq .80$, and a two-tailed test. Binary variables assessed under the same testing conditions would require an $OR \geq 5.95$.

Data Analysis Overview. Analyses will be conducted with SPSS and SAS version 9.4¹⁷⁴ and Mplus Version 7.¹⁷⁷ Descriptive statistics of demographics, smoking history, and alcohol history variables will be calculated and group comparisons will be performed. Descriptive statistics of all study measures (i.e., proximal and distal measures of alcohol use and smoking) will be calculated. Although underpowered to detect small- or medium sized sex differences, all analyses will examine sex as a covariate. Furthermore, analyses will include treatment group (i.e., each subset of participants who are treated with MBRP-SA or CBT together) when the intraclass correlation coefficient is > 0.10 .

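### The detectable effects stated for Study 2 (d of .72, odds ratio of 5.95 at 80% power) assume 64 independent participants, although both arms are treated in groups of 8 to 10

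*Combined protocol and SAP*

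**What the plan says.** The Sample Size paragraph (Data Management and Statistical Considerations for Study 2) justifies the total on feasibility grounds: "Randomizing 64 participants to MBRP-SA and CBT will provide sufficient data for assessing feasibility of the RCT". It then announces a full set of treatment-difference analyses and gives their limits: "the sample size will not be sufficient for detecting treatment differences for anything less than large effect sizes". The threshold it names is a Cohen's d of .72 when the two arms are compared on a continuous outcome, using a two-sided 5% test and at least 80% power. For binary outcomes, "Binary variables assessed under the same testing conditions would require an $OR \geq 5.95". It mentions no design effect, ICC, group structure or control rate.

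Two other places bear on this:

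- Both arms are treated in groups. The MBRP overview under Aim 1 gives 8 to 10 people per MBRP-SA group. The Aim 2 treatment description gives eight two-hour CBT sessions, "with 8-10 participants in each group".
- The next paragraph, Data Analysis Overview, provides for clustering conditionally: "analyses will include treatment group (i.e., each subset of participants who are treated with MBRP-SA or CBT together) when the intraclass correlation coefficient is" above 0.10.

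**The concern.** People treated together share a therapist and each other, so their outcomes may be correlated. If they are, 64 people carry less information about the treatment difference than 64 independent people, and the effect detectable with 80% power is larger than the one stated. The analysis paragraph recognises this possibility and the adjacent sample-size paragraph does not.

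Two uses of the figures are at stake. Readers of the treatment comparisons may take d = .72 as the effect the study had a good chance of finding, and read a null result accordingly. The plan also says that Study 2 will help to size a full-scale trial, and the independence calculation would be a poor template for another group-delivered trial.

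**Working it through.** **Inputs from the plan.** Total 64; two arms assigned in balanced blocks ("eligible participants will be assigned to the two treatments using balanced-permuted block randomization with a block size of 4"), so 32 per arm; two-sided alpha .05; power .80; d = .72; odds ratio 5.95; group size 8 to 10; ICC cut-off 0.10.

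**Assumptions.** 8 groups of 8 (4 per arm); all 64 analysed; ICC of .02, .05 or .10. Only 0.10 appears in the plan, as a modelling cut-off. The control rate for the odds ratio is not stated.

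**1. Reproduce the stated d.** With SD 1 and 32 independent people per arm, SE = √(2/32) = .25. The noncentrality is .72/.25 = 2.88. A noncentral t on 62 df gives power 80.9%, and the exact 80% threshold is d = .711. The stated .72 is correct for independent participants.

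**2. Reproduce the stated odds ratio.** The pooled two-proportion formula with 32 per arm gives a detectable odds ratio of 5.93 at a 10% control rate and 5.88 at 60%. At rates of 20% to 40% it gives 4.2 to 4.5. So 5.95 points to a rate near 10% or near 60%, and the plan does not say which.

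**3. Add the group structure.** DEFF = 1 + (8 − 1) × ICC; effective N = 64/DEFF; SE = √(2/32 × DEFF). For ICC .10: DEFF = 1.70, SE = .326, noncentrality = .72/.326 = 2.21. Power and detectable d come from the noncentral t, first on 62 df (design effect alone), then on 8 − 2 = 6 df (a test comparing group means).

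| ICC | DEFF | Effective N | Power at d = .72, 62 df | Detectable d, 62 df | Power at d = .72, 6 df | Detectable d, 6 df |
|---|---|---|---|---|---|---|
| 0 | 1.00 | 64 | 81% | .71 | 67% | .84 |
| .02 | 1.14 | 56 | 76% | .76 | 62% | .90 |
| .05 | 1.35 | 47 | 68% | .83 | 55% | .98 |
| .10 | 1.70 | 38 | 58.5% | .93 | 46% | 1.10 |

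A simulation of the group-means test at ICC .10 gave 46.2%, in agreement. On 62 df, d = .72 keeps 80% power only up to an ICC of about .003. On 6 df it falls short even at zero.

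**4. Larger groups.** With groups of 10 at ICC .10, DEFF = 1 + 9 × .10 = 1.90. Holding the same df, power at d = .72 is 54% (62 df) or 42% (6 df).

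**5. Odds ratio with clustering.** With 32/DEFF per arm in the same formula, the detectable odds ratio at ICC .05 and .10 is about 7.5 and 9.25 at a 10% control rate. At 60% it is about 9.6 and 18.4. The direction is certain; the size depends on the missing rate.

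**The case against.** The strongest reply is that the sentence is a disclaimer. It says that only large effects are detectable, and clustering makes that more true. Aim 3 is declared underpowered, the primary outcomes of Study 2 are the feasibility and acceptability benchmarks in Table 5, and 64 is not derived from d = .72. All of this stands, and it limits the weight of the point. It does not remove it: the disclaimer covers effects below the threshold and still names .72 as the effect with 80% power.

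A reader might go further in several directions that the documents do not support:

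- **That the trial's power is really about 46% to 60%.** That applies only at an ICC of 0.10, which the plan uses as a rule for when to model treatment group. It is neither a planning value nor a statement that correlation is expected.
- **That clustering explains the whole fall to 46%.** The plan specifies no 6-df group-level test. Choosing it accounts for the drop from 81% to 67% at an ICC of zero; the ICC of 0.10 accounts for the rest.
- **That either column is the power of the planned analysis.** At an ICC up to 0.10 the plan leaves treatment group out. An unadjusted t-test with groups of 8 and ICC .10 would reject about 75% of the time at d = .72. Its true type I error would be near 13% (critical value 1.96/√1.70 = 1.50; simulation 13.6%). The table therefore describes valid tests.
- **That the future trial will be undersized.** The plan says it will use observed means, SDs, percentages and confidence intervals. It does not say that this calculation will be carried forward.

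**Conclusion.** The point holds as an unstated independence assumption. The d is computed correctly for independent participants, and the odds ratio matches such a calculation at an assumed control rate; neither allows for group delivery. By the design effect alone, with 8 groups of 8 and complete data, the detectable d is about .83 at an ICC of .05 and .93 at .10, against the stated .72. With a 6-df group-level test it is about .98 and 1.10. At an ICC of .02 the design effect alone moves it only to .76.

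These sizes rest on assumed ICCs, equal groups of 8 and no dropout. The odds-ratio sizes also rest on an assumed control rate. The correction is worth making because the plan gives a specific number that its own group format undercuts. It does not affect the feasibility aims or the justification for 64 participants.

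**What to change.** Reword the Sample Size paragraph along these lines:

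> These thresholds (d of .72, odds ratio of 5.95) assume independent participants and essentially no correlation within treatment groups. With 8 groups of 8 and all 64 analysed, the detectable d would be about .83 at an assumed ICC of .05 and .93 at .10, or about .98 and 1.10 if tested at group level with 6 df.

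Label the ICCs as assumptions. State the control rate behind the odds ratio of 5.95, and add that this threshold also rises with clustering: to about 7.5 and 9.25 at ICCs of .05 and .10 if the rate is 10%. Avoid saying that the current figures hold only at an ICC of exactly zero, because that is true of neither test.

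The cost is a few sentences and a less favourable stated figure. No participants are added, and the design and feasibility aims stay as they are.
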